# **Study Summary**

Title	 C-Acetate PET/CT Imaging as a Marker of Amyloid-Induced Neuroinflammation			
Short Title	11C-Acetate PET/CT in neuroinflammation			
Protocol Number	IRB #824822			
Study Design	
 
Subjects will be part of one of the following cohorts:
 
Cohort 1: Patients with Mild Cognitive Impairment (MCI) (up to 14) will be recruited primarily from the Penn Memory Center (PMC). Clinical diagnostic criteria (described in further detail in Study Procedures section) will be used to identify subjects who are meet criteria for amnestic MCI.
 
Cohort 2: Normal control subjects in the same age range (up to 6) will be recruited from a current ongoing study investigating neuroinflammation in late life depression and healthy controls, from the control group in which all subjects receive MRI and LP (IRB 819654) and from the PMC research cohort.
 
Cohort 3: Cognitively normal subjects with a positive Amyloid PET (up to 5) may be recruited through other ongoing studies or PMC research cohort
 
			
	Screening assessments may take place over several days and may include demographic information, neurocognitive testing, with focus on language and visuospatial/ visuoperceptual measures; if available within 6 months of the study entry these tests may not be repeated. Amyloid brain PET/CT scan (required for Cohort 1 and Cohort 3 only) will be completed within 6 months prior to the  C-Acetate PET/CT, these scans may be done as part of this research protocol or they may be completed as part of another research study or clinical care, the images and reports for these scans will be reviewed. If the Amyloid brain PET/CT is done as part of this research study it will be done according to standard clinical procedure, using the FDA approved amyloid radiotracer,  F-Florbetaben (Neuraceq).			
	If the subject does not have a Brain MRI that is deemed acceptable for use for this study within 6 months of  C-Acetate PET/CT they will be asked to undergo a research Brain MRI after they have consented for this study.			
	Positron emission tomography/Computed Tomography (PET/CT) imaging will be used to evaluate the brain using the investigational radiotracer  C-Acetate. All patients will undergo a dynamic brain PET/CT scan approximately 60 minutes starting at the time of injection of  C-Acetate.			
Chudu Cartari(a)	Some subjects may be asked to undergo an optional cerebrospinal fluid (CSF) collection by lumbar puncture (LP) for additional research testing. Subjects have already undergone CSF collection clinically or as part of another study will not be asked to repeat these procedures.			
Study Center(s)	University of Pennsylvania			
Objectives	Primary Objective			
	Evaluate whether  C-acetate uptake is increased in amyloid positive Mild Cognitive Impairment (MCI) subjects compared to amyloid negative healthy controls			

# **Secondary Objectives** Correlate 11C-acetate uptake to areas of greater amyloid plague burden quantified on Amyloid PET/CT Compare C-acetate in areas of mildly elevated PET SUVR to areas with high or sub-threshold amyloid burden • Correlate C-acetate uptake to levels of inflammatory markers in CSF Up to 30 subjects may be enrolled, however, if a subject in the MCI cohort Number of Subjects undergoes an Amyloid brain PET/CT scan as part of this study and it is deemed negative that subject will be considered non-evaluable and will be withdrawn from the study and replaced in the enrollment. The target enrollment is 25 evaluable subjects. Inclusion Criteria for Cohort 1: (amnestic MCI) Diagnosis and Main Inclusion Criteria 1. Participants will be at least 55 years of age An Amyloid brain PET/CT is required. If a Amyloid brain PET/CT has been performed within 6 months of enrollment to this study and of adequate quality that scan may be used for the study analysis, subjects who do not have a Amyloid brain PET/CT will undergo an Amyloid brain PET/CT as a part of this study 2. Mini-mental status examination (MMSE) score ≥ 24 at screening visit 3. A brain MRI is required. If a brain MRI has been performed within 6 months of C-Acetate PET/CT and of adequate quality that scan may be used for the study analysis, subjects who do not have a brain MRI will undergo a brain MRI as a part of this study 4. Participants must identify a study partner who is willing to accompany the patient to study visits 5. Participants must be informed of the investigational nature of this study and provide written informed consent in accordance with institutional and federal guidelines prior to study-specific procedures. If the patient is unable to provide informed consent, the patient's legal representative may consent on behalf of the patient but the patient will be asked to confirm assent. **Inclusion Criteria for Cohort 2 (Normal Control)** 1. Participants will be at least 55 years of age 2. History of negative brain amyloid PET/CT scan within 6 months of study screening OR negative CSF analysis for AD biomarkers within 6 months of study screening 3. Mini-mental status examination (MMSE) > 27 at screening visit 4. A brain MRI is required. If a brain MRI has been performed within 6 months of enrollment to this study and of adequate quality that scan may be used for the study analysis, subjects who do not have a brain MRI will undergo a brain MRI as a part of this study 5. Participants must be informed of the investigational nature of this study and provide written informed consent in accordance with institutional and federal guidelines prior to study-specific procedures. **Inclusion Criteria for Cohort 3 (Cognitively normal Amyloid positive)** 1. Participants will be at least 55 years of age 2. History of positive brain amyloid PET/CT scan within 6 months of study screening Mini-mental status examination (MMSE) > 27 at screening visit

	4. A brain MRI is required. If a brain MRI has been performed within 6 months of enrollment to this study and of adequate quality that scan may be used for the study analysis, subjects who do not have a brain MRI will undergo a brain MRI as a part of this study			
	
 
Participants must be informed of the investigational nature of this study and provide written informed consent in accordance with institutional and federal guidelines prior to study-specific procedures.
 
			
	Exclusion Criteria (for both cohorts)			
	Inability to tolerate or contraindication to imaging procedures (PET/CT or MRI) in the opinion of an investigator or treating physician			
	
 
History of stroke or other neurological disease that in the opinion of the investigator might interfere with evaluation of the C-Acetate scan
 
			
	
 
Any medical or psychological conditions that, in the opinion of the investigator, would compromise the subject's safety or successful participation in the study.
 
			
Study Product	[  C]Acetate			
Statistical Methodology	Several methods for acetate binding quantification will be tested and compared; optimal quantification will be the simplest model that shows strong correlations between acetate binding and amyloid SUVR.  C-Acetate binding and amyloid SUVR will be analyzed using PMOD for modeling and static uptake estimates and Statistical Parametric Mapping using T1 MRI for co-registration and template-based regional segmentation. We will compare and correlate amyloid and acetate quantification using both Pearson's correlation and non-parametric Spearman's correlation.			
	The expected positive correlation between acetate binding and CSF cytokine levels will be evaluated. Global, regional and voxel based correlations will be performed between acetate uptake and amyloid PET SUVR from MCI subjects. Acetate binding in voxels with amyloid SUVR below, between 100-125%, or above 125% of previously validated thresholds  will also be compared.			

This document is a protocol for a human research study. This study is to be conducted according to US and international standards of Good Clinical Practice (FDA Title 21 part 312 and International Conference on Harmonization guidelines), applicable government regulations and Institutional research policies and procedures.

# 1. Background

# 1.1. Investigational Agent

C-Acetate is a radiolabeled imaging agent that has been used for studying tumor cells, myocardial oxidative metabolism and also has been shown to quantify astrocyte activation with positron emission tomography (PET/CT). Acetate metabolism has long been linked to astrocyte activation brain metabolism is highly compartmentalized and acetate is actively taken up by astrocytes and used for energy metabolism and lipid synthesis. The latter mechanism accounts for trapping of radiolabel in C-Acetate

PET/CT³ which can be quantified by both static uptake measures and kinetic analysis. This approach has been used to demonstrate astrocyte activation in multiple sclerosis  and alcoholism . Acetate PET/CT allows quantification of astrocyte activation without perturbing brain metabolism due to the tracer doses used for PET/CT, operating well below physiologic substrate concentrations.

This proposed protocol will test C-Acetate PET/CT as a marker for astrocyte activation associated with pathologic amyloid deposition in AD. Validating neuroinflammation markers in AD ultimately may guide therapeutic modulation of beneficial and damaging inflammatory responses to slow disease progression, as well as providing new insights into AD pathophysiology.

#### 1.2. Rationale

Alzheimer disease (AD), the most common neurodegenerative cause of dementia, affects millions of Americans with prevalence that will dramatically increase as the population ages. AD is associated with two abnormal protein aggregates: amyloid plaques and tau neurofibrillary tangles, which spread across the brain as the disease progresses, however the precise mechanism of pathogenesis remains unknown. A likely precipitant or accelerant of AD neurodegeneration is neuroinflammation. Glia, including astrocytes, which have myriad functions to support neuron and brain function, are mediators of neuroinflammation. Prior studies suggest that inflammation may have beneficial and detrimental effects on the brain. Astrocytes were noted to be increased in AD in the original observations by Alois Alzheimer, and subsequently demonstrated to be both associated with amyloid plaque and displaying ability to degrade them. Thus, reactive astrocytosis may be in part beneficial. However, chemokine-induced inflammation, which induces activation of microglia, the macrophages of the CNS, also causes neuronal damage.

Efforts to image neuroinflammation in AD have recently intensified . Based on the precedent of amyloid PET/CT, which profoundly increased our understanding of the biology of AD, and the emergence of tau PET/CT, such efforts are likely to provide critical understanding of the link between proteinopathy and neuroinflammation in AD pathophysiology. Much effort thus far has investigated the Translocator protein (TSPO), expressed by microglia , including showing an inflammatory response the predementia Mild Cognitive Impairment (MCI) phase of AD. However, targeting microglia does not investigate the full spectrum of neuroinflammation, particularly the potentially beneficial astrocyte response.

Our proposed study aims to use C-acetate PET/CT to preliminarily test and validate methods for imaging astrocyte activation as an early indicator of neuroinflammation in AD. C-Acetate PET/CT has been shown to quantify astrocyte activation *in vivo*, but no reports have evaluated its potential in AD. We propose to test C-Acetate PET/CT as a marker for astrocyte activation associated with pathologic amyloid deposition in AD. We will compare binding between subjects with early stage AD and cognitively normal subjects with positive Amyloid PET and healthy controls. Further, we will investigate the correlation between amyloid and acetate binding. If we find increased astrocyte activation in response to cerebral amyloid by showing a group difference in brain acetate uptake between disease and controls or a strong correlation between acetate and amyloid PET/CT binding. Validating neuroinflammation markers in AD ultimately may

guide therapeutic modulation of beneficial and damaging neuroinflammation to slow disease progression, as well as providing new insights into AD pathophysiology.

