# 2. Study Objectives

## 2.1. Primary Objective

 Evaluate whether C-acetate uptake is increased in amyloid positive Mild Cognitive Impairment (MCI) subjects compared to amyloid negative healthy controls

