# 2.2. Secondary Objectives

- Correlate C-acetate uptake to areas of greater amyloid plaque burden quantified on Amyloid PET/CT
- Compare C-acetate in areas of mildly elevated PET SUVR to areas with high or sub-threshold amyloid burden
- Correlate C-acetate uptake to levels of inflammatory markers in CSF

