# 3. Study Design

Subjects will be part of one of the following cohorts:

- Cohort 1:Patients with Mild Cognitive Impairment (MCI) (up to 14) will be recruited primarily from the Penn Memory Center (PMC). Clinical diagnostic criteria (described in further detail in Study Procedures section) will be used to identify subjects who are meet criteria for amnestic MCI.
- Cohort 2: Normal control subjects in the same age range (up to 6) will be recruited from a current ongoing study investigating neuroinflammation in late life depression and healthy controls, from the control group in which all subjects receive MRI and LP (IRB 819654) and from the PMC research cohort.
- Cohort 3: Cognitively normal subjects with a positive Amyloid PET (up to 5) may be recruited through other ongoing studies or PMC research cohort

Screening assessments may take place over several days and may include demographic information, neurocognitive testing, with focus on language and visuospatial/ visuoperceptual measures; if available within 6 months of the study entry these tests may not be repeated. Amyloid brain PET/CT scan isrequired for Cohort 1 and Cohort 3 only, subjects in Cohort 2 may have an Amyloid PET that has been done as part of standard care or another study but this is not required for entry into Cohort 2- In order to reduce costs, subjects may be recruited from other studies that perform amyloid PET/CT (typically with F-florbetaben or F-florbetapir) or have this test performed clinically. The CMS coverage

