Positron emission tomography/Computed Tomography (PET/CT) imaging will be used to evaluate the brain using the investigational radiotracer C-Acetate. Imaging will be performed using a dedicated PET/CT scanner (Philips Medical Systems, Netherlands). The protocol will be performed under the regulatory approval of the IRB and FDA IND that is held by the University of Pennsylvania, Department of Radiology. All patients will undergo a dynamic brain PET/CT scan including approximately 60 minutes of imaging starting at the time of injection of C-Acetate. All images will be reconstructed using standard reconstruction techniques. Standardized uptake value ratio (SUVr), the ratio of regional to reference uptake, will be calculated with cerebellum as reference. The cerebellum does not show amyloid accumulation until very advanced stages of AD.

Some subjects may be asked to undergo an optional cerebrospinal fluid (CSF) collection by lumbar puncture (LP) for additional research testing. Subjects have already undergone CSF collection clinically or as part of another study will not be asked to repeat these procedures.

We anticipate enrolling up to 25 participants total (14 in Cohort 1 MCI cohort, 6 in Cohort 2 normal control cohort, 5 in Cohort 3 cognitively normal amyloid positive) who meet eligibility requirements for this study. Accrual will likely occur over approximately 2 years.

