### 8.3. Subject Population(s) for Analysis

The primary analysis population will consist of age matched cohorts of amnestic MCI patients and normal controls. Patients will be recruited from the clinical practices of Penn Memory Center, Frontotemporal Lobar Degeneration Center, or other clinics of the University of Pennsylvania Health System. All subjects with an C-acetate PET/CT will contribute to the primary analysis.

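### The promised comparison with amyloid-positive, cognitively normal subjects (Cohort 3) has no objective or analysis behind it, and the MCI-control contrast alone cannot attribute a difference to amyloid

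*Combined protocol and SAP*

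**What the plan says.** The title describes the tracer scan as "Imaging as a Marker of Amyloid-Induced Neuroinflammation". Section 1.2 (Rationale) makes two statements that bear on the group analysis. It announces a comparison of three groups: "We will compare binding between subjects with early stage AD and cognitively normal subjects with positive Amyloid PET and healthy controls". It also says that astrocyte activation in response to amyloid would be shown "by showing a group difference in brain acetate uptake between disease and controls or a strong correlation between acetate and amyloid PET/CT binding".

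The later sections are narrower:

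- **Section 2.1** asks whether "uptake is increased in amyloid positive Mild Cognitive Impairment (MCI) subjects compared to amyloid negative healthy controls". Cohort 3 is absent.
- **Section 2.2** lists a correlation of acetate with amyloid, a comparison of acetate "in areas of mildly elevated PET SUVR to areas with high or sub-threshold amyloid burden", and a correlation with CSF markers. None contrasts cohorts.
- **Section 3** plans "14 in Cohort 1 MCI cohort, 6 in Cohort 2 normal control cohort, 5 in Cohort 3 cognitively normal amyloid positive", and every subject has the dynamic acetate scan.
- **Section 8.1** sizes MCI against controls only.
- **Section 8.2** names no between-cohort test, even for the primary objective. It uses the Cohort 3 group in the acetate-amyloid correlations, together with MCI subjects. The Study Summary's version of those correlations mentions MCI subjects only.
- **Section 8.3** states "The primary analysis population will consist of age matched cohorts of amnestic MCI patients and normal controls". It closes by saying that all subjects with an acetate scan contribute to the primary analysis.

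**The concern.** Cohorts 1 and 2 differ in two respects at once. Cohort 1 is amyloid positive and has amnestic MCI. Cohort 2 is amyloid negative and cognitively normal. A difference in uptake between them could reflect amyloid, cognitive impairment with whatever accompanies it, or both. Cohort 3 is the one group in the design that separates the two factors: it is amyloid positive, yet enters on the same MMSE threshold as the controls. Section 1.2 says it will be compared, but the objectives and statistical plan do not follow this through.

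Two things are at stake. First, a positive primary result could be reported as an amyloid effect, as section 1.2 invites, when the contrast does not identify one. Second, the last sentence of section 8.3 leaves the handling of Cohort 3 open. Grouped by amyloid status it would join the MCI patients; grouped by cognition it would join the controls. The text permits either, so the choice could be made after the results are seen.

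**Working it through.** **Step 1. What each cohort contrast varies** (sections 3 and 4.1 to 4.3)

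| Cohort | Planned n | Amyloid | Cognition |
|---|---|---|---|
| 1 | 14 | positive (negatives withdrawn) | amnestic MCI, MMSE at least 24 |
| 2 | 6 | negative (PET or CSF) | normal, MMSE above 27 |
| 3 | up to 5 | positive | normal, MMSE above 27 |

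- Cohort 1 minus 2: amyloid and cognition both change.
- Cohort 3 minus 2: amyloid changes; the cognitive criterion is the same.
- Cohort 1 minus 3: cognition changes; both are amyloid positive, but nothing in sections 4.1 or 4.3 equalises amyloid burden.

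Only the first appears in the objectives.

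**Step 2. Whether another planned analysis supplies the missing contrast**

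The correlations in section 8.2 cover amyloid-positive subjects only. Controls cannot simply be added, because section 3 does not require an amyloid PET for Cohort 2. The comparison of voxels below, at 100-125% of, and above 125% of the amyloid threshold bears on amyloid, but it compares tissue and not cohorts.

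**Step 3. The plan's own figure**

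Section 8.1 gives a detectable difference of 15% for 14 versus 6 with a precision of 20%. It states no alpha, sidedness, power or test. I read the 20% as a between-subject SD and assume two-sided 5%, 80% power and a t-test. The SE is 20 × √(1/14 + 1/6) = 20 × 0.488 = 9.76, and the detectable difference is 28.9%. The 15% would need an SD of about 10% (10.4%), so I show SD 10% and 20% below. That mismatch is a separate matter and this point does not rest on it. Section 8.1 gives no figure for Cohort 3.

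**Step 4. Precision of the contrasts from one three-cohort model**

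Residual df = 14 + 6 + 5 − 3 = 22, and t(0.975, 22) = 2.074. The 95% half-width is 2.074 × SD × √(1/n₁ + 1/n₂), in percentage points.

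| Contrast | √(1/n₁ + 1/n₂) | SD 10% | SD 20% |
|---|---|---|---|
| Cohort 3 − 2 (5 v 6) | 0.606 | 12.6 | 25.1 |
| Cohort 1 − 3 (14 v 5) | 0.521 | 10.8 | 21.6 |
| Cohort 1 − 2 (14 v 6) | 0.488 | 10.1 | 20.2 |

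Adding age leaves 21 df (t = 2.080). The Cohort 3 − 2 half-width at SD 20% becomes 25.2, before any loss from age imbalance. The difference detectable with 80% power for Cohort 3 − 2 is 17.8% at SD 10% and 35.5% at SD 20% (22 df). From those two cohorts alone (9 df) it is 19.1% and 38.1%.

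**The case against.** The strongest reply is that this is a pilot, the primary objective asks whether uptake is raised and not why, and section 1.2 offers the correlation as an alternative route to the amyloid claim. Much of this stands.

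- **The amyloid question is not left unaddressed.** A reader might infer that the study as a whole cannot support an amyloid effect. The documents do not support that. The voxel-threshold comparison, if made within subject, holds cognitive status fixed and includes sub-threshold tissue. The limit applies to the group contrast.
- **Cohort 3 is not wasted.** A reader might infer that its scans serve no purpose. Section 8.2 uses them in the global, regional and voxel correlations.
- **Atrophy is partly handled.** Section 7.1 applies partial volume correction, so atrophy should not be ranked as an equally likely explanation.
- **Section 8.3 might already include Cohort 3.** Its last sentence can be read so. It assigns no role, however, and conflicts with the sentence that defines the population.
- **The added contrasts are weak.** A half-width of 13 to 25 points cannot apportion a 15% difference, and section 3 says "Cohort 3: Cognitively normal subjects with a positive Amyloid PET (up to 5) may be recruited through other ongoing studies or PMC research cohort", so the cohort may be smaller than 5.

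The last item is a reason to label the estimates exploratory, not to omit them. Cohort 3 − 2 is only moderately less precise than the primary contrast (25.1 against 20.2 points at SD 20%), and section 8.1 gives sizing a larger study as a purpose of the pilot. Descriptive cohort summaries would meet the bare promise of section 1.2; a single model also gives intervals for the differences, at almost no extra cost.

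**Conclusion.** The concern holds for the group comparison. Section 1.2 promises a three-group comparison and reads a disease-control difference as a response to amyloid. Sections 2, 8.1 and 8.2 specify no contrast with Cohort 3, and section 8.3 contradicts itself on whether Cohort 3 enters the primary analysis. As written, the MCI-control contrast alone cannot attribute a difference to amyloid.

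A reader might try to put a figure on how much of an observed 15% difference is due to amyloid, say between none and all of it. The documents give no basis for such bounds: impairment or other pathology could raise or lower uptake, and sampling error would come on top.

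The precision figures (about 13 points at SD 10% and 25 at SD 20% for 5 versus 6 subjects) rest on reading the stated 20% precision as an SD, on equal variance across cohorts, and on full recruitment of Cohort 3. The change is worth making, but it does not put the primary objective itself in doubt.

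**What to change.** 1. **Section 2.2:** add an exploratory secondary objective to estimate differences in acetate uptake between Cohort 3 and each of the other cohorts.
2. **Section 8.2:** specify one linear model of acetate uptake on three-level cohort, with age as covariate. Report Cohort 3 minus Cohort 2 and Cohort 1 minus Cohort 3 with 95% confidence intervals, labelled as estimates. Note that Cohort 1 minus Cohort 3 may still reflect differing amyloid burden. Keep Cohort 1 versus Cohort 2 as the primary contrast.
3. **Section 8.3:** reconcile the two sentences by stating that Cohort 3 is not pooled into either arm of the primary contrast.
4. **Section 8.1:** state the expected precision as a range over the assumed SD (10% to 20%), and say that Cohort 3 may fall short of 5.
5. **Section 1.2:** limit the inference, so that a primary difference alone is not read as a response to amyloid.
6. **Study Summary:** align its description of the correlations with section 8.2 on whether Cohort 3 is included.

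The cost is a few lines of text and one model on scans already planned. The drawback is wide intervals, which the plan should acknowledge in advance.
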